This is an open label trial. Treatment will be conducted on either the left or right knee, thigh, arm, or ½ the abdomen, depending upon which area has the most cellulite or skin laxity. The contra-lateral side will not be treated and will serve as a control. A comparison of baseline photographs (prior to treatment) to photographs taken 1, 3 and 6 months after the completion of treatment will be conducted. Photographic equipment and the protocol for photography will be consistent at each visit. Ultrasound may be taken at baseline and at the follow-up visits to evaluate flatness of cellulite and dermal fibrosis or enlargement of the reticular dermis. Non-invasive light measurements may also be taken at baseline and follow-up visits. These do not hurt or pose a risk to the subjects and are similar to shining a flashlight on the skin and measuring the light. The area treated will be measured with a tape measure, weight/height will be recorded and the Body Mass Index (BMI) will be calculated at baseline and follow-up visits. In addition, skin elasticity may be measured at the treatment areas at baseline and follow-up visits. The photographs, ultrasound and measurements will be taken using consistent procedures at each visit by viewing the baseline photograph and using landmarks such as freckles and birthmarks.

The laser system to be used in this clinical study, Candela GentleYAG, a 1064 nm Nd:YAG laser is a commercially available laser and has been cleared by FDA under K022923, K022951, K023193 and K033172.

The Candela GentleYAG is cleared for removal of unwanted hair, for stable long term or permanent hair reduction and for treatment of pseudofolliculitis barbae, and is indicated on all skin types Fitzpatrick I-VI including tanned skin. The GentleYAG is cleared for treatment of vascular lesions such as port wine stain birthmarks, telangiectasia, rosacea, and leg and spider veins, and is cleared for treatment of benign pigmented lesions such as lentigos (age spots), café au lait birthmarks, and tattoos. The laser is also indicated for treatment of red pigmentation in scars with vascularity, and for treatment of wrinkles.

The Candela DCD produces a brief, timed spray of cryogenic fluid that evaporates from the skin surface and cools the epidermis, prior to each laser pulse. The DCD has been cleared by the FDA for minimizing pain and cooling the epidermis during laser treatment (K953412). The DCD is part of the Candela GentleYAG laser system.

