This is a pilot trial; therefore there is no basis for the sample size needed to determine a significant difference.

- 4. For multi-center research, indicate the overall sample size for the entire project (across all sites).
- [x] Not applicable This study is not a multi-center study.

B. Inclusion and Exclusion Criteria

1. Describe the **characteristics** of the proposed subject population (age, gender, health status, language, etc.)

Male or female \geq 18 years of age.

- 2. Provide the inclusion and/or exclusion criteria for the proposed subject population, as applicable.
- [] Not applicable This is not a clinical investigation and/or characteristics of the population sufficiently describe the proposed subject population.

Inclusion Criteria

- 1. Male or female \geq 18 years of age
- 2. Cellulite on the arm, knee, thigh or abdomen at stage 2 3 of cellulite per Nurnberger-Muller scale.
- 3. Subject is not overweight per B.M.I. criteria (B.M.I < 27).
- 4. Subject has Fitzpatrick skin phototype I-IV.
- 5. Subject is willing to participate in study and adhere to follow-up schedule.
- 6. Subject has signed the Informed Consent Form.

Exclusion Criteria

- 1. Subjects that have cellulite at stage 0-1 per Nurnberger-Muller Scale (the doctor will determine this)
- 2. Subjects that have had liposuction or other surgical procedures (including Mesotherapy) to remove fat on the proposed treatment area during the past year.
- 3. Subject has severe cellulite with referral to pain and/or tenderness on the area to be treated (Texture Scale: edematous).
- 4. Subject is overweight (BMI \geq 27).
- 5. Subject has known photosensitivity or history of ingesting medications known to induce. photosensitivity in the previous 3 months.
- 6. Subject has a personal or family history of keloid formation or of scarring.
- 7. Subject is pregnant or lactating.
- 8. Subject has a history of uncontrolled diabetes, and/or who requires medication which may interfere with the study.
- 9. Subjects with a known history of neuropathy.
- 10. Subjects with a known history of a coagulopathy.
- 11. Subject is unable or unwilling to comply with the study requirements.
- 12. Subject has a pacemaker or metallic implants.
- 13. Subject has Fitzpatrick skin type V and VI.
- 14. Subject is mentally incompetent or a prisoner.

3. If inclusion/exclusion is based on age, gender, pregnancy/childbearing potential, or race/ethnicity, provide a scientific rationale.

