Pregnant women are more prone to hyperpigmentation of the skin in response to laser treatments of all types and thus, they will be excluded.

We will enroll Fitzpatrick types I-III because although the 1064nm laser is indicated for all skin types, previous studies using the 1064 nm laser have noted that skin types IV and V experience more pain during treatment and are significantly more likely to develop skin dyspigmentation.

SECTION 5: RECRUITMENT METHODS AND PROCESS

A. Recruitment Methods

Please check all applicable recruitment methods that apply to the study. Place an "**X**" in the bracket [] next to the recruitment method.

- [] This study involves no direct contact with subjects (i.e., use of existing records, charts, specimens)
 - Skip to Section 6.
- [x] UCI IRB approved advertisements, flyers, notices, and/or media will be used to recruit subjects.
 - Passive Recruitment Potential subjects initiate contact with the study team.
 - Complete Question 5B Explain where recruitment materials will be posted.
- [] The study team will recruit potential subjects who are unknown to them (e.g., snowball sampling, use of social networks, direct approach in public situations, random digit dialing, etc.)
 - Active Recruitment Researchers contact potential subjects.
 - Complete Question 5B.
- [X] The UCIMC Clinical Trials web page will be used.
 - Passive Recruitment Potential subjects initiate contact with the study team.
 - Skip to Section 6.
- [] The UCI Social Sciences human subject pool will be used.
 - Passive Recruitment Potential subjects initiate contact with the study team.
 - Skip to Section 6.
- [x] Study team members will contact potential subjects who have provided permission to be

contacted for participation in future research studies.

- Active Recruitment Researchers contact potential subjects.
- Complete Question 5B Explain when and how these individuals granted permission for future contact; provide the IRB protocol numbers, if applicable.
- [x] Study team members will approach their own patients, students, employees for participation in the study.
 - Active Recruitment Researchers contact potential subjects.
 - Complete Question 5B.
- [] Study team members will send UCI IRB approved recruitment materials (e.g., recruitment flyer, introductory letter) to colleagues asking for referral of eligible participants.*
 - Passive Recruitment Potential subjects initiate contact with the study team or

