Subjects who believe they meet the exclusion and inclusion criteria and remain interested in the study will be invited to come in for their screening visit. During the screening visit, the investigator will ask the subject questions in order to determine if the inclusion and exclusion criteria are met. Following the investigator's determination that the inclusion and exclusion criteria are met, the subject will be invited to participate in the study. No data about the subject will be recorded until informed consent and HIPPA Authorization have been obtained.

This study will be posted on clinicaltrials.gov

SECTION 6: INFORMED CONSENT PROCESS

Describe the specific steps for obtaining informed consent.

- Include information about when and where consent will take place and the length of time subjects are given to decide whether they wish to participate.
- If study team members will approach their own patients, students, or employees for participation in the study, explain what precautions will be taken to minimize potential undue influence or coercion, and how compromised objectivity will be avoided.

Check all that apply:

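### The eligibility criteria admit Fitzpatrick type IV, while the protocol's own safety rationale says types I-III will be enrolled and names type IV as higher-risk

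*Protocol*

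**What the plan says.** All the statements in conflict are in Protocol Section 4B.

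- Inclusion criterion 4: "Subject has Fitzpatrick skin phototype I-IV".
- Exclusion criterion 13: "Subject has Fitzpatrick skin type V and VI".
- Item 3, the scientific rationale for the criteria: "We will enroll Fitzpatrick types I-III because although the 1064nm laser is indicated for all skin types". The reason given is that earlier studies with this wavelength noted that "skin types IV and V experience more pain during treatment and are significantly more likely to develop skin dyspigmentation".

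Two other places matter. The device description ahead of the Treatment Procedure section says the laser "is indicated on all skin types Fitzpatrick I-VI including tanned skin". Section 5B (Recruitment Process) sets out how a subject enters: "Following the investigator's determination that the inclusion and exclusion criteria are met, the subject will be invited to participate in the study". Section 6 repeats that rule.

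**The concern.** The rationale exists to justify the criteria, yet it describes a narrower population than they admit. The difference is a phototype that the rationale itself names as being at greater risk. Two things are at stake.

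**Subject protection.** The site will apply the numbered criteria. A type IV subject passes them and can be treated, although the protocol submitted for full committee review (Section 7A) says that types I-III will be enrolled, on grounds of pain and pigment change. Section 7B adds that the skin changes listed there may be permanent.

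**Interpretation of the safety results.** Hyperpigmentation and hypopigmentation are graded by the investigator at follow-up, and pain is rated on a 0-10 scale immediately after treatment. These are the harms that the rationale links to types IV and V. The observed frequencies will therefore depend on how many type IV subjects enter, and the protocol leaves it unclear whether any should.

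A lesser point is that visible pigment change on one side could show the photograph panel which side was treated. That risk exists for every phototype, and type IV would at most add to it.

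**Working it through.** There is no stated figure to reproduce. The protocol has no sample size calculation ("This is a pilot trial; therefore there is no basis for the sample size needed to determine a significant difference"), and none is needed here. The check compares the passages.

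**Step 1: compare the ranges.**

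| Source in Section 4B | Phototypes |
|---|---|
| Inclusion 4, admitted | I, II, III, IV |
| Exclusion 13, removed | V, VI |
| Item 3, to be enrolled | I, II, III |
| Item 3, named as higher-risk | IV, V |

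The two criteria agree with each other and leave I, II, III and IV eligible. Eligible minus to-be-enrolled leaves IV. The overlap between eligible and named as higher-risk is also IV. The phototype in dispute is thus the one flagged for risk.

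**Step 2: ask whether a single misprint explains it.** If the rationale meant to say I-IV, its reason would no longer support it, because it would admit type IV while giving type IV's higher risk as the ground for restriction. Both the range and the list of higher-risk types would need changing. If the criteria are wrong instead, both Inclusion 4 and Exclusion 13 need changing. Neither reading is a one-character slip, and the text does not show which was intended.

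**Step 3: look for a resolving statement elsewhere.** The device indication for types I-VI does not settle the matter, because the rationale acknowledges it and restricts enrolment all the same. The Pre-Treatment Procedure has skin type recorded but sets no further rule on it. Sections 5B and 6 tie the invitation to the listed criteria. No safeguard specific to type IV appears in the text.

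**Step 4: consider the possible effect on an observed rate.** The protocol gives no inputs, so the rates here are assumptions for illustration only. With dyspigmentation of 5% in types I-III, 20% in type IV, and a share *s* of type IV subjects:

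overall rate = (1 − *s*) × 5% + *s* × 20% = 5% + 15% × *s*

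- *s* = 0: 5%
- *s* = 0.25: 0.75 × 5% + 0.25 × 20% = 8.75%
- *s* = 1: 20%

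On the target of 24 subjects (Section 4A), 5% is 24 × 0.05 = 1.2 subjects and 8.75% is 24 × 0.0875 = 2.1 subjects. The illustration shows how the rate would move with case mix. It does not estimate the size of the problem, and the finding does not rest on it.

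**The case against.** The strongest reply is that the operative criteria are not ambiguous. Inclusion 4 and Exclusion 13 agree, Section 5B makes them decisive, and the conflict is only with an explanatory paragraph. That paragraph names types IV and V but not VI, so it may simply be loosely drafted. This is fair as far as it goes. But if the criteria are right, the protocol admits a group it calls higher-risk and gives no reason for doing so. The text still needs correcting.

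Other points stand in part:

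- General precautions exist: optional test spots starting at low fluence, optional topical anesthetic, a cooling device, and bleaching cream if hyperpigmentation occurs. None is specific to type IV, and none removes the contradiction.
- Each subject's untreated side is the control, so phototype mix does not confound the treated-minus-untreated comparison. The consequence is confined to subject protection and the makeup of the safety data.
- The rates in the illustration are assumed, and a difference of about one subject in 24 could not be detected in a pilot of this size. That is correct, and the illustration carries no weight in the conclusion.
- Unmasking through visible skin reactions can occur in any phototype, and reconciling the range would not cure it. It does not support the severity of this point.
- Separate reporting for type IV would rest on few subjects and is not needed to remove the contradiction. It could also be specified in an analysis plan that is not at hand.

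**Conclusion.** The concern holds and must be fixed. As written, type IV is eligible under the criteria and outside the enrolled population under the rationale for them, and nothing else in the protocol resolves this. It affects every type IV subject who presents, on a safety ground the protocol itself states. How many that would be, and by how much their risk differs, cannot be derived from the document.

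The conclusion rests only on the wording of Section 4B and on the rule that enrolment follows the listed criteria. One inference is involved: the rationale does not use the word only, but a statement that types I-III will be enrolled because of the risks in IV and V can hardly be read otherwise. The documents do not settle which range is intended, and no view on that is taken here.

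**What to change.** Reconcile Inclusion 4, Exclusion 13 and Section 4B item 3 so that all three name the same phototypes.

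- If type IV is to remain eligible, the rationale must stop stating I-III and must justify admitting a type it describes as having more pain and dyspigmentation. Pain and pigmentation outcomes should then also be listed separately for type IV, as description only.
- If type IV is not to be enrolled, both criteria must be changed to match the rationale. Changing one alone would leave a new conflict.

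The amendment should be in place before any further subject is enrolled under these criteria. The protocol carries a 2006 study number and a 2009 approval date and does not say whether enrolment has begun. If it has, the number of type IV subjects already treated should be stated with the amendment.

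The cost is a short text change to either the two criteria or the rationale, plus its review. Recruitment may slow slightly if the range narrows. No sample size calculation is affected, because there is none.

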Appendix P.

- [x] Written (signed) informed consent will be obtained from subjects. Explain below.[] Requesting a waiver of written (signed) informed consent. Explain below and complete
- [] Requesting a waiver of informed consent (no consent). Complete Appendix O. Skip to Section 7.

Subjects who believe they meet the exclusion and inclusion criteria and remain interested in the study will be invited to come in for their screening visit. During the screening visit, the investigator will ask the subject questions in order to determine if the inclusion and exclusion criteria are met. Following the investigator's determination that the inclusion and exclusion criteria are met, the subject will be invited to participate in the study.

The Informed Consent document will be reviewed with the subject and signed if the subject understands and accepts the document. The estimated time for the review and the explanation of the consent form is about 30 minutes. The subject will be enrolled in the study after signing the informed consent. After signing the consent, the subject is enrolled.

 Non-English Speaking Participants: In order to consent subjects who are unable to read and speak English, the English version of the consent form must be translated into appropriate languages once IRB approval is granted.

Check all that apply:

- [] Not applicable Only individuals who can read and speak English are eligible for this study.
- [x] The English version of the consent form will be translated into appropriate languages for non-English speaking subjects once IRB approval is granted. Note: The IRB must stamp the translated consent forms before they are used. An interpreter will be involved in the consenting process.
- [] Requesting a short form consent process. Complete Appendix Q.

SECTION 7: RISK ASSESSMENT AND POSSIBLE BENEFITS

Review of the instructions for this section is strongly recommended.

A. Risk Assessment

Place an "X" in the bracket [] next to the level of review (based upon the investigator's risk assessment).

- [X] This study requires full committee review.
- [] This study qualifies for **exempt or expedited review** status. List the applicable exempt or expedited category(ies) and provide justification for the level of review and for the category(ies) chosen in the space below:

<Type here>

B. Risks and Discomforts

- 1. Describe the **risks/potential discomforts** (e.g., physical, psychological, social, economic) associated with **each** intervention or research procedure.
- 2. Estimate the probability (e.g., chance or likelihood of occurrence) that a given harm may occur and its severity (e.g., mild, moderate, severe).

The possible risks and/or discomforts associated with the procedures described in this study include pain, purpura (bruising), edema, papule formation, erythema (redness), hyperpigmentation (darkening of skin), hypopigmentation (lightening of skin), blistering, crusting and scarring. Changes in the skin from any of the aforementioned risks may be temporary or permanent. A lesser possibility exists of pinpoint bleeding and infection associated with a wound from blistering or bleeding in the treatment area.

3. Discuss what measures have been taken and/or will be taken to **prevent and minimize** any risks/ potential discomforts.

The PI and colleagues have extensive experience in performance of laser treatments which will help to minimize risk. If hyperpigmentation occurs, bleaching cream can be used to minimize the effect.

- For Full Committee protocols, state whether any study procedures may involve risks to the subject (or embryo or fetus, if the subject is or may become pregnant) that are currently unforeseeable.
- [] Not applicable This study qualifies for Exempt or Expedited review.

It is possible that the laser treatment could involve risks that are currently unforeseeable. Because laser light penetrates only a few millimeters into the skin, risk to a fetus is unlikely. However, because the risk to a fetus is unknown, pregnant women will be excluded.

C. Potential Benefits

- 1. Discuss the benefits that may accrue **directly to the subjects**. *Note: Compensation is not a benefit. Do not include it in this section.*
- [] There is no direct benefit anticipated for the subjects.

The possible benefits from the procedures described in this study include improvement in the appearance of cellulite and/or tightening of thigh skin.

2. Describe the potential societal/scientific benefit(s) that may be expected from this study.

This study may allow us to provide better treatments for cellulite in the future.

[figure not shown]
D. Risk/Benefit Assessment

For **Expedited and Full Committee protocols**, explain why the study risks are reasonable in relation to the **potential benefits** to subjects and society.

[] Not applicable - This study qualifies for Exempt review; there is virtually no risk/potential discomfort to the subjects.

Nd:YAG laser treatment has been shown to be a safe and effective treatment for many conditions on various body locations, including laser-based hair removal in the thigh area. As such, the risk of injury is relatively low and there is the potential benefit of improvement in the appearance of cellulite.

SECTION 8: ALTERNATIVES TO PARTICIPATION

B. Compensation for Injury

For Full Committee protocols, explain how costs of treatment for research related injury will

be covered.
[] Not applicable - This study qualifies for Exempt or Expedited review.
[x] Subjects who are injured as a direct result of their participation in this study will be provided reasonable and necessary medical care to treat the injury at no cost to them or their insurer/third party payer. The University of California does not routinely provide any other form of compensation for injury.
[] Other: <type here=""></type>
SECTION 10: PARTICIPANT COSTS
Identify and estimate those costs to be borne by subjects or their insurers, including costs of standard medical interventions or procedures.
[] Not applicable - This study involves no subject contact (i.e., use of existing records, charts, specimens).
[X] There are no costs to subjects/insurers.
<type here=""></type>
SECTION 11: PARTICIPANT COMPENSATION AND REIMBURSEMENT
If subjects will be compensated for their participation, provide detailed information about the amount and the method/terms of payment (e.g., money; check; extra credit; gift certificate). In addition:
 Describe the schedule of compensation (e.g., at end of study; after each session/visit). Compensation should be offered on a prorated basis. Specify whether subjects will be reimbursed for out-of pocket expenses. If so, describe any requirements for reimbursement (e.g., receipt).
[] Not applicable - This study involves no subject contact (i.e., use of existing records, charts, specimens).
[X] No compensation will be provided to subjects.

[] No reimbursement will be provided to subjects.

<Type here>

SECTION 12: CONFIDENTIALITY OF RESEARCH DATA

Explain how data will be collected and recorded.
Data Collection/Method of Recording (check all that apply):
 [X] Paper documents/records [] Computer files/database [] Audio recording [] Video recording [X] Photographs [] Biological specimens [] Other(s) (specify): <type here=""></type>
 Indicate whether subject identifiers will be linked (directly or indirectly via a code) to the research data.
[] No Subject Identifiers will be collected (i.e., the data are anonymous; no one, including the study team, can link subjects to their data)
[X] Indirect link to Subject Identifiers (i.e., a code will be assigned to the data and a key linking the code to the identity of the subjects exists)
[] Direct link - Subject Identifiers will be maintained with data (i.e., personal or private information about the subjects are associated with the data)
List the direct identifiers here: <type here=""></type>
[] Other (explain here): <type here=""></type>
 Indicate how data will be stored, secured including paper records, electronic files, audio/video tapes, specimens, etc. NOTE: The more sensitive the study data, the more sophisticated the methods should be to maintain confidentiality.
Electronic Data (check all that apply): [] Anonymous or de-identified data only [] Coded data with the code key kept in separate location [] Encryption or password protection software [X] Secure network server [] Stand alone desktop computer (not connected to server/internet) [] Other (specify here): <type here=""></type>
Hardcopy Data, Recordings and Specimens (check all that apply): [] Anonymous or de-identified only [X] Locked file cabinet or locked room at UCI/UCIMC

19 (
[] Locked lab/refrigerator/freezer at UCI/UCIMC[] Other (specify here): <type here=""></type>
 4. Data on portable devices: Describe the portable device(s) to be used (e.g. laptop, PDA). Specify whether subject identifiable data will be stored on the device. If so, justify why it is necessary to store subject identifiers on the device. Note: only the "minimum data necessary" should be stored on portable devices.
[X] Not applicable – No study data will be maintained on portable devices. <type here=""></type>
Specify who will have access to subject identifiable data and records.
[] Not applicable – No subject identifiers will be collected. [X] The research team, authorized UCI personnel, the study sponsor (if applicable), and regulatory entities such as the Food and Drug Administration (FDA) and the Office of Human Research Protections (OHRP), may have access to study records to protect subject safety and welfare. Any study data that identifies the subjects will not be voluntarily released or disclosed without the subjects' separate consent, except as specifically required by law. Publications and/or presentations that result from this study will not include subject identifiable information.
[] Other: <type here=""></type>

6. Explain how long the research data (hard copy documents, computer files, recordings) will be **retained** once the research has been completed (e.g., destroyed upon study completion; stored for future research; retained for a specified timeframe, etc.)

Note: If your study involves the creation of a research database, specimen repository, or you plan to share data or specimens for secondary uses or analyses, Appendix M is required.

The researchers intend to keep the research data for approximately 5 years.

7. Certificates of Confidentiality:

- Specify whether a Certificate of Confidentiality (COC) has been requested from the NIH.
- If yes, explain in what situations personally identifiable information protected by a COC will be disclosed by the UCI study team.

Note: A copy of the COC should accompany the IRB application or be provided to the IRB upon receipt.

[X] Not applicable – No COC has been requested for this study.

<Type here>
